 - who, in the clinical opinion of the Patient Eligibility Review Committee or Investigator, is not an appropriate candidate for sub-retinal surgery (see the Patient Eligibility Review Plan)
5. Have participated in another research study involving an investigational product in the past 12 weeks or received a gene/cell-based therapy at any time previously, except if treated within in an antecedent study with AAV2-REP1.

Test Product, Dosage, and Mode of Administration: For each eye, subjects will undergo vitrectomy and retinal detachment and receive a sub-retinal injection of up to 0.1 mL of study drug containing 1×10^{11} AAV2-REP1 genome particles (gp).

Reference Therapy (Comparator), Dosage, and Mode of Administration: Not Applicable.

Criteria for Evaluation:

Safety: The safety evaluation will be based on BCVA (as measured by the ETDRS chart); full ophthalmic examination (including IOP, slit lamp examination, lens opacity grading and dilated ophthalmoscopy); SD-OCT; fundus AF; fundus photography; microperimetry; AE reporting; vector shedding and immunogenicity; and vital signs.

Efficacy: The efficacy evaluation will be based on BCVA (as measured by the ETDRS chart); fundus AF; SD-OCT and microperimetry.

Statistical Methodology: No formal sample size calculation will be performed.

Continuous variables will be summarised over time using descriptive statistics (i.e., mean, standard deviation, 95% confidence intervals [CI], median, first and third quartiles, fifth and ninety-fifth percentiles, minimum, and maximum). Categorical variables will be described over time using counts, percentages, and 95% CIs. Summaries will be tabulated by visit and eye. No formal statistical testing will be performed.

AEs will be summarised by system organ class, preferred term, and eye. The number of eyes with an AE, as well as the number of events, will be summarised, by period and eye. Similar summaries will be produced for study drug/procedure-related AEs, AEs leading to discontinuation, and serious AEs. AEs will also be summarised by maximum severity, relationship to study drug/procedure, and time to onset and resolution. Vector shedding and immune response profiles will be described.

The remaining safety evaluations will be analysed using descriptive statistics.

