13.6.7 Adverse Events

AEs will be coded using the Medical Dictionary for Regulatory Affairs, version 21.0 or higher. Events will be summarised by system organ class and preferred term and eye. The number of eyes with an AE, as well as the number of events, will be summarised, by period and eye. Similar summaries will be produced for study drug/procedure-related AEs, AEs leading to discontinuation, and SAEs. AEs will also be summarised by maximum severity, relationship to study drug/procedure, and time to onset and resolution.

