4.10 Disposition of Subjects

The number of subjects who sign Informed Consent, who receive study treatment, who complete the study and the reasons for any premature discontinuation from the study will be presented. The number of subjects included in the All Treated Subjects analysis set and the Immunogenicity analysis set will also be presented. For each study visit, the number of subjects who attend the visit will be summarised.

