4.17.10 Adverse Events

Treatment Emergent Adverse Events (TEAEs) are defined as AEs starting on or after the day of the first surgery. AEs reported in subjects who received timrepigene emparvovec treatment in their first eye in an antecedent study will be considered as TEAEs. Where an AE start date is partially or fully missing, and it is unclear as to whether the AE is treatment emergent, it will be assumed that it is. Summary tables will include TEAEs only. TEAEs will be summarised by eye (for ocular events), by period, and overall. Each by-period summary table will be repeated by surgery window instead.

The number and percentage of subjects reporting any event, any non-ocular event, any ocular event, any ocular event in SE1 and any ocular event in SE2 will be summarised. Percentage will be calculated based on the number of subjects in the corresponding period or surgery window or overall. The 95% CI will be calculated using the Clopper-Pearson method.

Overall summary table of TEAE by period (or by surgery window) will be provided for the following categories:

- Number and percentage of subjects with a TEAE
- Number and percentage of subjects with a serious TEAE
- Number and percentage of subjects with a Treatment-related (study drug or study procedure) TEAE
- Number and percentage of subjects with a Treatment-related (study drug or study procedure) serious TEAE
- Number and percentage of subjects with a TEAE leading to death
- Number and percentage of subjects who discontinued due to a TEAE
- Number and percentage of subjects with a TEAE by severity
- Number and percentage of subjects with a TEAE by outcome
- Number and percentage of subjects with a TEAE by action taken

Adverse events will be summarized by period (or by surgery window), and overall. The following summaries of TEAEs will be provided:

- TEAEs by SOC and PT
- TEAEs by PT with percentage $\geq 5\%$
- Treatment-related (study drug or study procedure) TEAEs by SOC and PT
- Study procedure-related TEAEs by SOC and PT
- Study drug-related TEAEs by SOC and PT
- TEAEs by SOC, PT, and maximum severity (missing severity, if any, will be counted as severe).
- Serious TEAEs by SOC and PT
- Treatment-related (study drug or study procedure) serious TEAEs by SOC and PT
- Study procedure-related serious TEAEs by SOC and PT
- Study drug-related serious TEAEs by SOC and PT
- TEAEs leading to death by SOC and PT
- TEAEs reported by subjects who discontinued due to SAE by SOC and PT

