Both counts of subjects and events will be reported. A subject with more than one occurrence of the same AE in a particular SOC will be counted only once in the total of those experiencing AEs in that particular SOC.

If a subject experiences the same AE at more than one severity, the most severe rating will be given precedence.

If a subject experiences the same AE at more than one relationship to study drug/procedure, causal relationship will be given precedence over no causal relationship. However, where a causal relationship is identified by the Investigator, the subject will be counted once within each sub-category (Study Drug, Study Procedure, Study Drug and Study Procedure, unknown).

In the summary tables, related events are defined as events that are assessed by the investigator to be related to study drug/procedure/both or with an unknown relationship.

AEs will be assigned to Period 1 or Period 2 based on the AE Start Date. An AE with a start date on or after the day of surgery of Study Eye 2 will be attributed to Period 2; otherwise, the AE will be attributed to Period 1.

An ocular event is an event where the site of the event is reported as OU, OD or OS. Where an event is recorded as 'OU', it will be counted once for each eye (SE1 and SE2).

Separate additional summaries will be provided for adverse events classified as Ocular Inflammation and Visual Acuity Reduced. The lists of PTs assigned to Ocular Inflammation and Visual Acuity Reduced are provided in a separate document (BIIB111 Signal Detection Plan). The following summaries will be provided by eye, by period (or by surgery window), and overall:

- Ocular Inflammation-related TEAEs by SOC and PT
- Ocular Inflammation-related TEAEs by SOC and PT, and by time to onset (≤ 30 days; > 30 days)
- Visual Acuity Reduced-related TEAEs by SOC and PT
- Visual Acuity Reduced-related TEAEs by SOC and PT, and by time to onset (≤ 30 days; > 30 days)

Imputation rules for partial dates are presented in Appendix 7.1.

The following listings will be provided:

- All AEs
- AEs leading to death

AEs will be coded according the MedDRA version 23.0 or higher.

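### The SAP's only SOC/PT discontinuation table is limited to subjects who left because of an SAE and tabulates all their TEAEs, whereas the protocol plans summaries of the AEs that led to discontinuation, serious or not

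*SAP*

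**What the plan says.** **Protocol.** After describing AE summaries by SOC, PT and eye, with counts of eyes and events, section 13.6.7 states: "Similar summaries will be produced for study drug/procedure-related AEs, AEs leading to discontinuation, and SAEs". The synopsis makes the same commitment: "Similar summaries will be produced for study drug/procedure-related AEs, AEs leading to discontinuation, and serious AEs". In both places discontinuation and seriousness are separate items, and neither limits the other.

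**SAP 4.17.10, overall TEAE table.** Two rows bear on this point: "Number and percentage of subjects who discontinued due to a TEAE" and "Number and percentage of subjects with a TEAE by action taken". Both count subjects. Neither gives a SOC or PT.

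**SAP 4.17.10, detailed summaries.** One line concerns discontinuation: "TEAEs reported by subjects who discontinued due to SAE by SOC and PT". The line directly above it reads "TEAEs leading to death by SOC and PT".

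**SAP 4.17.10, listings.** Two are planned: one of all AEs, and one described as "AEs leading to death".

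**SAP 4.10, disposition.** The section covers the number of subjects "who complete the study and the reasons for any premature discontinuation from the study will be presented".

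**SAP 4.20, changes from the protocol.** Four changes are declared. The one on AEs drops time to resolution. The discontinuation table is not mentioned.

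**The concern.** The SAP line departs from the protocol's item in two directions. It is narrower in subjects, because the reason for leaving must have been an SAE. It is broader in events, because it takes the TEAEs those subjects reported, whether or not they had anything to do with leaving.

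Safety is the study's only objective, and AE reporting is one of its primary safety measures. Which events cause subjects to leave a bilateral gene therapy study is a basic tolerability result. With the table as specified, a reader could take events that caused no withdrawal for reasons for withdrawal, and would find no summary that names the non-serious reasons as such.

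**Working it through.** No arithmetic in the plan needs to be reproduced, because the point rests on no sample size, rate or error level. The check compares the texts and then asks whether the planned outputs agree with each other.

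**1. Can a non-serious AE be a reason for discontinuation?** Yes. Protocol 8.3 allows withdrawal for an AE that leaves the subject unable to keep up with study assessments. It does not require the AE to be serious.

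**2. Which planned outputs in SAP 4.17.10 and 4.10 would show it?**

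| Output | Covers a non-serious cause? | Gives SOC/PT? | Marks the term as the cause? |
|---|---|---|---|
| Overall table, discontinued due to a TEAE (1 of 9 categories) | Yes | No | No term shown |
| Overall table, action taken (1 of 9) | Yes | No | No term shown |
| Disposition reasons (4.10) | Yes | No, as described | No term described |
| General TEAE table by SOC and PT (1 of 12) | Yes | Yes | No |
| Discontinuation table (1 of 12) | No, unless the subject left because of an SAE | Yes | No, all TEAEs of the subject are included |
| Listing of all AEs (1 of 2) | Yes | Content not specified | Not specified |
| Listing of AEs leading to death (1 of 2) | Not its purpose | – | – |

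No row combines all three properties.

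**3. Is the wording deliberate?** The death line directly above uses event-level wording: it takes the events with that outcome. The discontinuation line instead takes a group of subjects and then their events. The SAP therefore has the event-level form available and does not use it here.

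**4. Do the outputs reconcile?** Let S be the number of subjects who discontinued because of a serious TEAE, and N the number who discontinued because of non-serious TEAEs only. The overall row counts S + N subjects. The SOC/PT table contains S. The gap is (S + N) − S = N, and no planned summary by term explains it. If a subject in S reported k TEAEs of which c led to discontinuation, the table shows k events for that subject, and k − c of them were not the cause. The two outputs agree on subjects only if N = 0. The table shows only causes only if k = c for every subject in S.

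**5. Is it a version effect?** The SAP states that it is based on the protocol dated 30 October 2019, version 4. The summary of changes for version 3 already gives the discontinuation item as revised text, and the current protocol still has it. A lag between documents is therefore not a likely explanation.

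**The case against.** **A reader might infer that non-serious causes disappear from the report, or have no term anywhere.** The documents do not support that. The overall row has no seriousness limit and is given by period or surgery window. Disposition presents the reasons. The event itself gets its SOC and PT in the general TEAE table, and it is in the listing of all AEs. Protocol 11.1.2 records the action taken for each AE, so with few cases a reader may be able to trace the term. The SAP does not say which columns the listing will show, so this cannot be settled. What is missing is only a summary that names the term as the cause.

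**The protocol commitment may be looser than it looks.** The sentence on similar summaries follows directly after one on counts of eyes and events, so it could refer to those counts and not to the SOC/PT layout. Protocol 13.4 leaves detailed specifications to the SAP. The SOC/PT reading is the natural one, since that layout opens the same paragraph, but it is not the only one. Even on the looser reading, a table that selects by SAE and takes all TEAEs is not a summary of AEs leading to discontinuation.

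**The line may be shorthand.** It may be meant as TEAEs leading to discontinuation, and the table shells are not available to decide. That is a fair point about intent. A programmer who follows the words would still produce the other table, and the SAE restriction would remain in either case.

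**A reader might infer that events unrelated to treatment are being mixed in.** That is a different matter. The extra events are ones that did not cause the discontinuation, and they may fall in any causality category.

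**The consequence is small.** This stands. Each eye receives a single injection, so only withdrawal from the study is at issue. Under Protocol 8.3, subjects whose second eye is not treated after a problem in the first eye should stay in Period 1 for safety follow-up, so they do not count as discontinuations for that reason. The analysis is descriptive, and no endpoint or denominator changes.

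**Conclusion.** The point holds in a limited form. The SAP contains no SOC/PT table of the events that led to discontinuation. The one it lists in that place leaves out subjects with non-serious causes only and, as worded, adds events that were not causes. The departure from Protocol 13.6.7 and the synopsis is not declared in SAP 4.20.

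The size is one table out of 12 detailed TEAE summaries. The number of subjects affected is unknown because the documents give no count of discontinuations. It may be small, but that would be an assumption. The conclusion rests on reading the SAP line as written and on taking the protocol's item as not limited to serious events, which its separate mention of SAEs supports. It does not mean that the report hides non-serious withdrawals: their number and reasons are still presented.

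**What to change.** In SAP 4.17.10, replace the line with a summary of *TEAEs leading to study discontinuation by SOC and PT*. It should include serious and non-serious events and count only the event or events that led to discontinuation, with a serious subset if wanted. The subject total should then agree with the overall row. A matching listing, parallel to the one for deaths, would help. If the present table is intended, declare and justify it in SAP 4.20 and state which events enter it.

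The cost is one revised table, and one short listing if it is added. No new data are needed: the reason for withdrawal is recorded in the eCRF (Protocol 8.3), as is the action taken for each AE (Protocol 11.1.2), and the overall row already requires the SAP to identify subjects who discontinued due to a TEAE.

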11.1.2 Recording of Adverse Events

AEs/SAEs will be collected from the time the subject provides written informed consent (Screening Visit) through Period 2, Visit 9 (Month 12 ± 14 Days or ET Visit, if applicable).

Subjects will be questioned on the occurrence of an AE at every visit including any unscheduled visit, by using non-leading questioning such as 'How have you been since the last visit?'

All AEs occurring during the study observed by the Investigator or reported by the subject, whether or not attributed to study drug or the surgical procedure, will be recorded in the subject's medical records and in the eCRF. Any clinically significant changes in laboratory results or vital sign measurements (as determined by the Investigator) are to be recorded as an AE.

Ocular AEs are to be recorded on a per-eye basis.

The following information will be recorded in the eCRF for each AE: description, date of onset and end date, outcome, severity, assessment of relatedness to study drug/study procedure, the action taken and confirmation of whether the event is considered serious (see [Section 11.1.1.2](#) for the definition of seriousness). Follow-up information should be provided as necessary (see [Section 11.1.3](#) for specifics on follow-up procedures).

AE severity and relationship to the study drug or the surgical procedure will be assessed at the site by the Investigator or a medically qualified designee.

AE Severity

The severity of events will be assessed on the following scale:

- 1 = mild (awareness of sign or symptom, but easily tolerated)
- 2 = moderate (discomfort sufficient to cause interference with normal activities)
- 3 = severe (incapacitating, with inability to perform normal activities).

AE Relationship

When assigning relatedness of the AE, consideration will be given to whether there is a plausible relationship to either the study drug or the surgical procedure. The following are definitions of relatedness that will be used in this study:

Unrelated: The event is not reasonably related in time to the administration of the study drug/surgical procedure, or exposure of the study drug/surgical procedure has not yet occurred, or biologic plausibility does not exist

Related: A reasonable possibility exists that the study drug / study procedure caused the AE. A suspected AE can be further defined by:

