3.1 Discussion of Study Design

This is a Phase 2, multi-centre, open-label, prospective, 2-period, bilateral interventional safety study of timrepigene emparvovec in adult male subjects with genetically confirmed CHM.

The study will consist of a Screening Period followed by 2 treatment periods (Period 1 and Period 2) with up to 9 visits per treatment period. A second baseline visit prior to surgery of Study Eye 2 (SE2) (Period 2, Visit 1) may be required. A study schematic is presented in [Figure 1](#).

Figure 1 Overall Study Schematic

During the Screening Period, subjects will be assessed for eligibility of both eyes. The investigator will assign the order in which the eyes are treated (i.e., study eye 1 [SE1] period 1 and study eye 2 [SE2] period 2, respectively) with a number assigned to each eye. This will be done in collaboration with the subject; however, the worse eye will generally be selected for first treatment. The estimated target interval between the surgical procedures of SE1 and SE2 will be determined at the Screening Visit.

Each study eye will be followed for at least 12 months post-treatment, for up to 9 visits per treatment period: Visit 1 (Day 0, Injection Day Visit); Visit 2 (Day 1, post-operative follow up visit); Visit 3 (Day 3 + 2 Days); Visit 4 (Day 7 -1/+2 Days); Visit 5 (Day 14 ± 3 Days); Visit 6 (Month 1 ± 7 Days); Visit 7 (Month 3 ± 14 Days); Visit 8 (Month 6 ± 14 Days) and Visit 9 (Month 12 ± 14 Days).

The interval between SE1 and SE2 treatment is expected to vary among subjects from weeks to many months. While the interval will be decided on a case-by-case basis, an effort will be made to schedule varying treatment intervals in order to better characterise the immunological and safety profile of sequential treatment administration. Thus, approximately 20 subjects each will be treated with a short- (<6 month), medium- (6-12 months), or long- (>12 month) surgery window between treatment of the first and second eye. Because the timing of the second surgery visit (Period 2, Visit 1) will vary among subjects, the duration of study Period 1 will also be variable.

All baseline ophthalmic assessments must be conducted within 3 months prior to SE2 surgery (Period 2, Visit 1). If these assessments are not available within the required timeframe, a Baseline Visit must be added to collect current baseline data on SE2. If, at that time, BCVA in SE2 is <34 ETDRS letters, surgery may be performed when, in the opinion of the

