4.3 Definitions

Study Eye 1 (SE1) is defined as the first treated eye (within GEMINI or in an antecedent clinical trial). **Study Eye 2 (SE2)** is defined as the second treated eye (irrespective of whether the first eye was treated in GEMINI or in an antecedent clinical trial). Subjects whose first eye is treated in an antecedent study will contribute to Period 2 only (except for the immunogenicity analyses), where Study Eye 1 is the eye treated in the antecedent study and Study Eye 2 is the eye treated in GEMINI.

Period 1 starts on the day of the surgery of the first treated eye and ends on the day prior to the day of the surgery of the second treated eye. **Period 2** starts on the day of the surgery of the second treated eye.

Baseline Value of Period 1/2 is defined as the last non-missing value prior to treatment of the respective period. Baseline of each period for each eye will be used to calculate the change from baseline for the data in the same period and same eye. For example, period 1 SE1 baseline will be used to calculate the change from baseline for all the data of SE1 in period 1, whereas period 2 SE1 baseline will be used to calculate the change from baseline for all the data of SE1 in period 2.

For immunogenicity, baseline will be defined separately in [Section 4.17.11](#).

Analysis day for all the post-baseline visits will be calculated as the date of the post-baseline visits minus the corresponding injection date, depending on which baseline that was used.

For the 6 subjects whose first eye was treated in the antecedent study (Subjects [REDACTED], [REDACTED], [REDACTED]), only period 2 data are collected in GEMINI. Therefore, only period 2 data will be presented for these 6 patients.

Change from Baseline is defined as the difference of the value of an assessment at the considered visit from the baseline value of the corresponding period.

Duration is measured in days and is calculated as end date – onset date + 1.

Injection dates of SE1 and SE2 will be coded **Day 0** for the Period 1 and Period 2 respectively.

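### By-period adverse event percentages set a first-eye window of variable length beside a nominal 12 months for the second eye, and no planned AE table puts both eyes on the same time since their own surgery

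*SAP*

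**What the plan says.** SAP 4.3 defines Period 1 as running from first-eye surgery; it "ends on the day prior to the day of the surgery of the second treated eye". The later period opens with that second operation. SAP 3.1 plans about 20 subjects in each of three intervals between surgeries (under 6, 6 to 12 and over 12 months), so "the duration of study Period 1 will also be variable". Protocol 9.8 provides for second surgery before Day 21.

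Under Protocol 11.1.2, "AEs/SAEs will be collected from the time the subject provides written informed consent (Screening Visit) through Period 2, Visit 9", which is Month 12 ± 14 days, or to the early termination visit.

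SAP 4.17.10 assigns events to periods: "An AE with a start date on or after the day of surgery of Study Eye 2 will be attributed to Period 2". On denominators: "Percentage will be calculated based on the number of subjects in the corresponding period or surgery window or overall". Ocular events are also shown by eye. The surgery-window tables replace the period split and are not crossed with it. SAP 4.15 does not evaluate exposure, and no person-time rate is planned for AEs.

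Three provisions bear on time since an eye's own surgery:
- **SAP 4.17.10** splits Ocular Inflammation and Visual Acuity Reduced events at 30 days from onset.
- **SAP 4.17.11.4** repeats that split, by assay status, for those two groups and for hypersensitivity events.
- **SAP 4.16.1** remaps SE1 BCVA from Period 2 onto visits counted from SE1 surgery, using the Period 1 baseline. SAP 4.17.1 puts the letter-loss categories in the same tables.

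**The concern.** Someone asking whether the second treatment is as safe as the first will look at SE1/Period 1 beside SE2/Period 2. The second is observed for about 12 months. The first is observed for as long as the subject happened to wait for second surgery, yet each subject counts once in the denominator whatever the time at risk.

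Take a subject re-dosed at Month 3 who develops a cataract in SE1 at Month 5. The event keeps its SE1 label but leaves the Period 1 column and appears after the second dose. The overall SE1 column does not help, because it runs for the interval plus 12 months. The 30-day split gives a nearly matched early window for subjects re-dosed after Day 30, but only for the named event groups. Its late category has no Month 12 limit, and SAP 4.17.10 does not say from which surgery onset is counted for an SE1 event in Period 2.

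At stake is the descriptive safety reading of first against second treatment, in a study whose objective is the safety of sequential bilateral administration.

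**Working it through.** The plan gives no expected AE percentage by period, so there is no stated figure to reproduce. The check asks what the tables would show if both eyes carried exactly the same risk.

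**From the documents:** the three interval bands, about 20 subjects each (SAP 3.1); a nominal 12-month Period 2 (Protocol 11.1.2); 6 antecedent-study subjects who contribute to Period 2 only (SAP 4.3).

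**Assumed:**
- intervals uniform on 21-182, 183-365 and 366-548 days;
- Period 1 weights of 20/20/20, or 20/20/14 if all 6 antecedent subjects belong to the long band;
- a true 12-month risk r of 20% in each eye.

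**1. Length of Period 1.** The band means are 101.5, 274 and 457 days, or 3.3, 9.0 and 15.0 months. The pooled mean is 277.5 days (9.1 months) for 20/20/20. For 20/20/14 it is (20×101.5 + 20×274 + 14×457)/54 = 257.6 days (8.5 months). Period 2 has 12 months.

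**2. Share of SE1's first-year risk filed in Period 2, constant hazard.**
- Short: 1 − 101.5/365 = 72%.
- Medium: 1 − 274/365 = 25%.
- Long: 0%.
- Pooled: (72.2 + 24.9 + 0)/3 = 32%, or (20×72.2 + 20×24.9)/54 = 36%.

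If half the hazard falls in Days 0-30, the pooled share is 18-20%.

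**3. Percentage shown for SE1/Period 1.** Let H = −ln(1 − r) = 0.223. A subject with interval T days has probability 1 − exp(−H(T)) of an event in Period 1. With a constant hazard, H(T) = H×T/365. With a share f of the hazard in the first 30 days, H(T) = fH×T/30 up to Day 30, then fH + (1 − f)H×(T − 30)/335. Averaging over the assumed intervals gives:

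| Timing of risk | Short | Medium | Long | Pooled | SE2/Period 2 |
|---|---|---|---|---|---|
| Constant | 6.0% | 15.4% | 24.3% | 14.2-15.2% | 20% |
| Half in first 30 days | 12.6% | 17.5% | 22.4% | 17.0-17.5% | 20% |
| 75% in first 30 days | 16.3% | 18.8% | 21.2% | 18.5-18.8% | 20% |

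**4. Sensitivity to the intervals.** With fixed intervals, equal weights and a constant hazard, the ratio SE2/Period 2 to SE1/Period 1 should be 1.00. It comes out as:
- 1, 6 and 12.5 months: Period 1 shows 1.8%, 10.6% and 20.7%, mean 11.0%; ratio 1.81.
- 3, 9 and 15 months: 5.4%, 15.4% and 24.3%, mean 15.1%; ratio 1.33.
- 5.9, 12 and 24 months: 10.4%, 20.0% and 36.0%, mean 22.1%; ratio 0.90.

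The middle ratio hardly depends on r: it is 1.33 at 5.1% (the visual-acuity-reduced frequency in Protocol 5.4) and 1.32 at 30%. Across the three interval sets, the ratio is 0.96 to 1.14 with 75% of the risk in month 1, and 0.98 to 1.05 with 90%.

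**5. Can a common window be built?** A completer with both eyes treated in GEMINI has SE1 AE follow-up of the interval plus about 12 months. Counting each eye over the same 12 months from its own surgery gives a ratio of 1.00 under equal risk.

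**The case against.** - **No comparison is planned.** SAP 4.2 rules out formal comparison, and no section says the by-period tables are meant for inference on first against second dose. SAP 3.6 attaches its key concern to the immunological profile, not to an AE contrast. This stands and limits the harm to descriptive misreading.
- **Vision loss is largely covered.** SAP 4.16.1 and 4.17.1 let SE1 letter loss be read from SE1's own surgery. This stands for BCVA. It does not extend to AE tables or to events such as cataract.
- **Post-surgical events may cluster early.** If they do, the gap is small, as the 75% row shows. This stands; event timing is not in the documents.
- **The cut at second surgery is defensible.** Period 1 is the only window free of second-dose exposure, and SAP 4.17.11.1 recognises that second treatment may raise the risk of an immune response. An SE1 event after SE2 surgery may therefore reflect either dose. This stands, so an own-surgery table cannot simply replace the period tables.

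A reader might infer that the tables make the first treatment look safer and the second worse. The documents do not support a fixed direction: the long band works the other way, SAP 3.1 sets no upper limit on it, and under Protocol 8.3 a subject whose second eye is not treated stays in Period 1. Nor is first-eye data collection cut short; only the by-period tabulation is.

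**Conclusion.** The point holds as a defect of presentation. Crude Period 1 and Period 2 AE percentages cover different times at risk, and no planned AE table corrects this over a common 12 months. With equal true risk of 20% and the assumed uniform intervals, SE1/Period 1 would show about 14-15%, 17-17.5% or 18.5-19%, depending on how early events occur, against 20% for SE2. The short band understates SE1 and the long band overstates it. The pooled sign depends on intervals that the documents do not give. The distortion matters most for late-onset events, such as cataract, and for short intervals. It is worth correcting because the data already exist, but it does not undermine the study.

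**What to change.** In SAP 4.17.10:

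1. Keep the by-period tables. Add subject-months at risk, or exposure-adjusted rates, to each column, including for non-ocular events, which an eye-level table cannot resolve.
2. Add a supplementary ocular TEAE table by eye, from Day 0 to Month 12 after that eye's own surgery, split into ≤30 days and >30 days to Month 12. Produce it for any, serious and related ocular TEAEs, Ocular Inflammation and Visual Acuity Reduced.
3. Restrict it to subjects with both eyes treated in GEMINI, and show SE2 of the 6 antecedent-study subjects separately.
4. Present SE1 twice: with all events to Month 12, and censored at SE2 surgery.
5. State that any comment on first against second treatment will draw on these tables together with the by-period tables, not on crude period percentages alone.

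The cost is SAP wording and a few extra tables, with no new data or subjects. Some ambiguity remains in attributing SE1 events after the second dose; showing both versions makes it visible but cannot remove it. SE1 of the antecedent-study subjects cannot be included.
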